4. STUDY PRODUCTS/MATERIALS

4.1 Description of Study Products

The following products will be used during this study.

- Subjects UB non-mentholated filtered king size cigarettes sourced by the subjects
- Subjects UB mentholated filtered king size cigarettes sourced by the subjects
- Non-mentholated very low nicotine (VLN) cigarettes sourced by 22nd Century Group, Inc
- Mentholated VLN cigarettes sourced by 22nd Century Group, Inc
-

VLN cigarettes contain 0.4 mg nicotine per gram of tobacco. Subjects will be provided with a supply of VLN cigarettes, up to 150 % of their usual daily consumption as reported during Week -1.

4.2 Study Product Accountability

Usual brand (UB) cigarettes will be provided by the study subjects. All VLN study products will be provided by the Sponsor. The pharmacy staff at the site will coordinate receipt of products from the subjects and the Sponsor. The pharmacy will document the date on which products were received and record this in the inventory records. The site pharmacy will document and reconcile the total number of products received at the site, the total number of products dispensed during the study, and the total number of products remaining at the end of clinical conduct.

Subjects will be instructed to not bring any tobacco- or nicotine-containing products into the clinic, other than UB cigarettes at the end of Week -1 visit or VLN cigarettes at the end of Weeks 2 and 6 visits. After their Week -1 visit, subjects assigned to the VLN groups will be requested only to smoke VLN cigarettes during all the clinic visits and the ambulatory periods.

All investigational products will be stored in locked, limited-access areas in the clinic site's pharmacies at controlled room temperature (defined as 20°-25°C [68°-77°F], with excursions permitted to 15°-30°C [59°-86°F]).

Individual study product dispensing records will be maintained by the site pharmacy for each subject. During clinic visits, used cigarette butts will be returned to the staff following each product use for accountability purposes and will be disposed of following accountability by the pharmacy staff. During ambulatory periods, used cigarette butts will be collected by subjects for the purposes of assessing cigarette consumption, checking compliance and study product accountability, and will be disposed of following accountability checking.

Unused VLN cigarettes will be disposed of as directed by the Sponsor. Unused UB cigarettes may be returned to the study subjects at the end of the study, according to site policy. All returns of products will be documented. Subjects will not return unused UB.

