On Day 1 of Week 1, subjects will be randomly selected to either remain smoking their non-menthol (20 subjects) or menthol (20 subjects) UB cigarettes, or to switch to smoking non-menthol (50 subjects) or menthol (50 subjects) VLN cigarettes as per their UB cigarette flavor. Subjects will return at the end of Weeks 2 and 6, at the time indicated by the CRU, for collection of blood and 24-hour urine samples for BoE assessments. Subjective effects questionnaires will also be completed at scheduled times. Subjects will continue recording their CPD in their e-diaries. A subset of 18 non-menthol and 18 menthol smoker subjects will complete an assessment of puffing topography with the VLN

cigarettes at these visits, and a further subset of 12 non-menthol and 12 menthol smoker subjects will also complete an assessment of nicotine PK at the end of these visits. Subjects undergoing topography and PK assessments will have been assigned to switch to smoking VLN cigarettes.

Additionally, all subjects will visit the clinic at the end of Week 4 to receive further supplies of cigarettes (if assigned to the VLN groups) and to complete subjective effects questionnaires.

Subjects randomized to the VLN groups will be provided with a supply of VLN cigarettes at each visit, which will be 150 % of their usual daily consumption as reported during Week -1. If a subject runs out of cigarettes between clinic visits, they may visit the clinic to receive additional test cigarettes. All subjects will be asked to smoke their cigarettes *ad libitum*, recording their actual daily consumption in their e-diaries. Non-compliant nicotine product consumption should also be recorded. Used cigarette butts will also be collected during ambulatory periods to verify product use and/or assess compliance. During Week -1 (all subjects) and all subsequent weeks (subjects randomized to continue smoking UB cigarettes) subjects will be asked not to change their UB cigarette brand or flavor.

The CRU will attempt to contact all subjects who participated in the study (including subjects who terminate the study early) using their standard procedures approximately 7 days after the last contact to determine if any AE has occurred since the last study visit.

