5.4 Clinic Visits (End of Weeks -1, 2 and 6)

Subjects will check in to the clinic at the end of Weeks, -1, 2 and 6 at times specified by the clinic. Subjects will be housed in the clinic until after the 24-hour urine collection and other study procedures. The following procedures will take place during this visit:

- Verification that inclusion and exclusion criteria have not been violated since last visit
- UB cigarette documentation for subjects assigned to continue smoking UB cigarettes
- Urine drug and alcohol screens
- Vital signs
- Urine pregnancy test for females
- Review of AEs and concomitant medication use.
- Usual brand cigarette documentation (only at Week -1).
- Return canister with used cigarette butts for counting
- 24-hour urine collection for BoE analysis
- Plasma sample for cotinine analysis
- Blood sample for carboxyhemoglobin (COHb) analysis
- Daily recording of CPD in the e-diary.
- Completion of subjective effects questionnaires
- Puffing topography assessment (subset of subjects)
- Nicotine PK assessment (subset of subjects)

- Dispense new canister for collecting used cigarette butts during next ambulatory period, except at Week 6
- Review smoking and nicotine product use restrictions
- Test product dispensing for the following ambulatory period; except at Week 6

All subjects will have their personal belongings thoroughly checked at the start of these clinic visits.

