5.9 Tobacco Product Use

Except as required by the protocol, consumption of tobacco- or nicotine-containing products will not be permitted during the entire duration of the study from the start of Week -1 through discharge from the study. During the baseline period, subjects will be asked to confine their smoking to one brand which will be deemed their UB. While in the CRU during 24-hour confinement periods, cigarette consumption will be tracked by the number of products dispensed.

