5.12.7 Product use recording

5.12.7.1 Electronic diary for cigarette consumption

Subjects will be provided with e-diaries to record their daily cigarette consumption, both when in clinical confinement during study visits and during ambulatory periods. Subjects will be instructed to record both compliant and non-compliant (if any) daily numbers of cigarettes smoked. Non-compliant consumption in the subjects randomized to smoke VLN cigarettes is defined as nicotine product consumption other than their UB cigarettes during the baseline period (Week -1) or VLN cigarettes following switching (Weeks 1 to 6). Non-compliant consumption in the subjects randomized to continue to smoke their UB cigarettes is defined as nicotine product consumption other than their UB cigarettes between Week -1 and Week 6.

For the purposes of data analysis, the e-diary record of cigarette consumption will be used as the primary variable.

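### Protocol 4.2 admits only VLN cigarettes at the Week 2 and 6 visits and makes no exception for the 40 subjects assigned to keep smoking their usual brand

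*Protocol*

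**What the plan says.** Protocol 4.2 gives one carry-in rule, addressed to subjects as a whole. Nothing containing tobacco or nicotine may be brought in, "other than UB cigarettes at the end of Week -1 visit or VLN cigarettes at the end of Weeks 2 and 6 visits". The next sentence, which asks that only VLN be smoked after Week -1, is limited to the VLN groups. The carry-in rule has no such limit. The same section states: "Usual brand (UB) cigarettes will be provided by the study subjects". Section 5.4 provides a check at check-in: "All subjects will have their personal belongings thoroughly checked at the start of these clinic visits".

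Section 2.1 has some subjects "remain smoking their non-menthol (20 subjects) or menthol (20 subjects) UB cigarettes", and asks every subject to smoke ad libitum. Both arms attend the later biomarker visits: "Subjects will return at the end of Weeks 2 and 6, at the time indicated by the CRU, for collection of blood" and 24-hour urine. Section 5.12.7.1 adds: "Non-compliant consumption in the subjects randomized to continue to smoke their UB cigarettes is defined as nicotine product consumption other than their UB cigarettes", from Week -1 to Week 6. Section 5.9 says that during the 24-hour confinements "cigarette consumption will be tracked by the number of products dispensed".

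SAP 8.4 analyses the biomarkers in two ways. Paired t-tests compare Weeks 2 and 6 with each group's own Week -1 value. The mixed model of SAP 7.3 then compares VLN with UB on change from baseline at the same visits.

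**The concern.** The UB arm is the trial's only concurrent control. Its baseline collection takes place at a visit where UB may be brought in. Read literally, 4.2 removes that permission at both later collections, and the search of belongings gives sites a reason to enforce it. A control subject could then enter a 24-hour urine and blood collection without the product that he or she is assigned to smoke.

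Change from baseline in that arm would then mix two smoking conditions. Part of any fall in a UB-arm biomarker would come from the clinic rule rather than from continued UB smoking, and the fall would be subtracted from the VLN effect in the between-group model.

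**Working it through.** The plan states no figure on this point. The check sets the sections side by side, followed by counts.

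**1. Does 4.2 conflict with other sections for the UB arm at Weeks 2 and 6?**

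- Assignment (2.1): these subjects stay on UB and smoke ad libitum. 4.2 lets them carry in only VLN.
- Compliance (5.12.7.1): the one product that 4.2 admits would be recorded as non-compliant if they smoked it.
- Pack documentation (Summary of Study Events and 5.4): UB documentation for this arm is scheduled at both visits, and a footnote says that it includes photocopying the pack. This presupposes a UB pack in the clinic.
- Blood biomarkers (5.12.4; SAP 8.2.1): the carboxyhemoglobin and cotinine draw requires a minimum of 30 minutes without product. That condition presupposes that smoking takes place during the visit, and no arm is excepted.

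**2. Is another UB supply stated?**

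- UB comes from the subjects (4.1, 4.2).
- Scheduled supplies of cigarettes go to the VLN groups (2.1).
- The only visit at which 4.2 admits UB is the end of Week -1. Section 2.1 places allocation after that, on Day 1 of Week 1. A stock left at that visit would have to be deposited before the subject's arm was known, and no section asks for this.

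So no supply is stated for these two confinements.

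**3. How much data is exposed?**

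Inputs are the arm sizes and visits in Protocol 2.1.

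- UB arm: 20 + 20 = 40. VLN arm: 50 + 50 = 100. Total: 140.
- UB share: 40/140 = 28.6%.
- UB-arm post-baseline collections: 40 × 2 = 80.
- All post-baseline collections: 140 × 2 = 280, and 80/280 = 28.6%.
- Including baseline: 140 × 3 = 420, and 80/420 = 19.0%.

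The 80 collections are all of the post-baseline reference data in the VLN-versus-UB model.

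**4. Direction of the bias**

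Let D be the true VLN reduction relative to UB, and f the extra fall in the UB arm caused by lack of cigarettes. The observed difference is D − f. The documents give neither value, so the figures below are assumptions for illustration, in percentage points.

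| D | f = 10 | f = 25 | f = 50 |
|---|---|---|---|
| 50 | 40 | 25 | 0 |
| 30 | 20 | 5 | −20 |

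The contrast shrinks toward zero as long as f does not exceed D.

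**The case against.** The strongest reply is that the sentence limits what subjects carry in, not what they smoke, and that much of the plan assumes UB is available. In 4.2 the pharmacy coordinates receipt of products from subjects, and unused UB may go back to them at the end of the study. Section 5.9 describes product being dispensed in confinement. The SAP listing shell for dispensed product (Appendix 16.2.5.2.2.1) has a field for naming the usual brand. The intended design is clear, and a sensible site might handle it correctly.

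Much of this stands. A reader might infer from 4.2 that UB controls would certainly have nothing to smoke. The documents do not support that certainty, because a site-held supply is possible. But none of these provisions says that UB is held or dispensed for the UB arm at Weeks 2 and 6. Section 4.2 also blurs the matter by saying, next to the provision for giving unused UB back to subjects, that subjects do not return unused UB. The stated rule still contradicts the rest of the plan, and two sites could resolve it differently.

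Three further readings go too far:

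- **A near-total loss of marker.** The 120-minute nicotine half-life in SAP 9.3.1 would make 24 hours equal to 12 half-lives, or about 0.02% remaining (2^-12). That constant serves the baseline adjustment of plasma nicotine, which is measured only in VLN-assigned subjects (Protocol 5.12.6). The documents give no half-life for the other markers, and the urine is pooled over 24 hours rather than sampled at the end.
- **Every biomarker contrast shrinks.** Without those half-lives, the effect on any single marker is unknown.
- **The UB arm is the reference for all biomarker analyses.** The paired tests within the VLN groups use each subject's own Week -1 value and no UB-arm data.

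**Conclusion.** Wrong as written. The carry-in rule in 4.2 contradicts the UB arm's assignment, its definition of compliance, its pack documentation and the blood-sampling condition, and no section supplies UB by another route at the Week 2 and 6 confinements.

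The consequence is conditional. It arises only if sites apply the sentence literally and hold no UB. In that case up to 40 of 40 controls at both visits, 80 of 280 post-baseline collections, could reflect reduced exposure. Within-UB changes would be distorted. The between-group biomarker comparisons, which serve a secondary objective, would be biased toward no difference, provided that the shortfall is no larger than the true difference. The amount of bias cannot be computed from the documents.

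**What to change.** Reconcile 4.2 with 2.1, 5.4, 5.9 and 5.12.7.1 by replacing the visit-specific list in 4.2 with an arm-specific rule: the product permitted at each confinement is the one the subject is assigned at that time. The sponsor should state which route applies to the UB arm at Weeks 2 and 6, either that subjects bring their own UB or that the site pharmacy holds and dispenses it. The two statements in 4.2 about unused UB should be made to agree with that choice.

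The cost is about one sentence in the protocol and the same sentence in the site instructions. Sample size, endpoints and analyses do not change.

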4.3 Labelling

The containers housing the VLN cigarettes will be labelled to include the following information:

- Study number
- Product identifier
- Administration requirements/handling directions
- Storage conditions
- Expiry date
- Sponsor's name and address
- Name of PI
- "For Clinical Trials use only"
- "Keep out of reach of children"

4.4 Blinding

This is an open-label study.

4.5 Randomization

A randomization scheme will be provided by Celerion for the clinical sites. A suitably qualified person will monitor the randomization to ensure the study groups are balanced in terms of age and gender, as far as practicable. Each study group will include no fewer than 10 subjects of either gender and no fewer than 10 subjects from each age group (\leq 40 years old and $>$ 40 years old).

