2.1 Design and Procedures

This is an open-label, non-randomized, forced-switching study to be conducted at multiple study sites. Seventy (70) self-affirmed exclusive filtered king size non-mentholated cigarette smokers and 70 self-affirmed exclusive filtered king size mentholated cigarette smokers will be enrolled and begin the study at Week -1.

All potential subjects will provide informed consent and successfully complete the Screening procedures prior to participation in the study. Subjects will also engage in a brief product trial with the VLN cigarettes. Subjects who react negatively (i.e., unwilling to use and/or cannot tolerate the product [experience adverse events (AEs) that will prevent them from continuing to use the product as judged by the Investigator]) to the VLN cigarettes during the product trial period will not continue in the study.

At the start of Week -1, all subjects will be asked to smoke their UB cigarettes as per their usual daily consumption for the following week. Subjects will receive an electronic diary (e-diary) to record daily cigarette use (cigarettes per day [CPD]). Training in completion of the e-diary will be provided at the visit at the start of Week -1.

Subjects will return at the end of Week -1, at the time indicated by the clinical research unit (CRU), for collection of blood and 24-hour urine samples for baseline BoE assessments. Subjective questionnaires for dependence, withdrawal symptoms, urges to smoke, and perceived health risk will also be completed at scheduled times. A subset of 18 non-menthol and 18 menthol smoker subjects will complete an assessment of puffing topography with their UB cigarettes during this visit. A further subset of 12 of the non-menthol and 12 of the menthol smoker subjects who complete the topography assessment will also complete a nicotine PK assessment at the end of this visit. Subjects who undergo topography and PK assessments will be assigned to switch to smoking VLN cigarettes.

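### Protocol 4.5 in effect requires an exact 10/10 split on sex and on age in each 20-subject UB group, and the only control it describes is a person monitoring an open-label randomisation

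*Protocol*

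**What the plan says.** Protocol 4.5 states that the contract research organisation will supply a randomisation scheme, and then: "A suitably qualified person will monitor the randomization to ensure the study groups are balanced in terms of age and gender". That duty is limited to what is practicable. The next sentence drops the qualifier: "Each study group will include no fewer than 10 subjects of either gender and no fewer than 10 subjects from each age group". The age groups are 40 or under and over 40.

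Protocol 2.1 enrols 70 smokers per flavour and selects them at random on Day 1 of Week 1 to "remain smoking their non-menthol (20 subjects) or menthol (20 subjects) UB cigarettes, or to switch to smoking non-menthol (50 subjects) or menthol (50 subjects) VLN" products. The same section has 18 subjects per flavour complete topography at the end of Week -1 as people who will be assigned to VLN, before that random selection. Protocol 4.4 reads: "This is an open-label study".

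Neither document names stratification factors, a block structure, minimisation, enrolment caps, a concealment method or who holds the list. Protocol 2.1 calls the study non-randomised; SAP 3 calls it randomised. The SAP 7.3 mixed model has product group, week and their interaction as fixed factors, with no term for sex or age.

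**The concern.** A minimum of 10 in both halves of a group of 20 leaves no slack. Once a UB group holds 10 men, the next man can only go to VLN. If the men still to come are just enough to reach 10, each of them must go to UB. Under the monitoring arrangement as written, late assignments are then either known in advance or changed by the person watching, who can see what has already been allocated.

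The comparison exposed to this is VLN versus UB. SAP 7.3 labels the pooled VLN versus pooled UB contrast as the primary one within the mixed model, and cigarettes per day is self-recorded in an unblinded study. Random allocation is one of the few protections that contrast has. In addition, a design that balances on sex and age is analysed by a model that leaves both out.

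**Working it through.** The plan gives no probability or method for meeting the minimum, so there is no figure to reproduce.

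**Inputs**
- Per flavour: 70 enrolled, 20 UB, 50 VLN (Protocol 2.1).
- Minimum of 10 per sex and 10 per age band in each study group (Protocol 4.5).
- Sex and age mix of those enrolled: not given. Assumed range 35/35 (most favourable) to 25/45. For age, eligibility is 26 to 65 (Protocol 3.1), so the younger band covers 15 of 40 years, or 37.5% if ages were spread evenly.

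**Step 1: permitted counts.** For UB, k ≥ 10 and 20 − k ≥ 10 leave only k = 10. For VLN, k ≥ 10 and 50 − k ≥ 10 allow 10 to 40, which chance meets essentially always. The rule binds only on the controls.

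**Step 2: one factor, one UB group, unrestricted allocation.** With K of 70 in one category, P = C(K,10) × C(70−K,10) / C(70,20).

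| Pool split | P(exactly 10 of 20) |
|---|---|
| 35/35 | 20.8% |
| 30/40 | 15.7% |
| 28/42 | 11.9% |
| 25/45 | 6.4% |

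**Step 3: both factors.** Let a, b be men in the younger and older bands, and c, d women in the same order. P = Σ over x = 0 to 10 of C(a,x) × C(b,10−x) × C(c,10−x) × C(d,x), divided by C(70,20). The two flavours are drawn separately, so the chance for both UB groups is the square.

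| Cells a/b/c/d | One UB group | Both UB groups |
|---|---|---|
| 18/17/17/18 | 4.3% | 0.19% (1 in 540) |
| 15/20/15/20 | 3.3% | 0.11% (1 in 939) |
| 12/23/12/23 | 1.0% | 0.01% (1 in 9,204) |

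**Step 4: sensitivity.** The first row assumes sex and age are nearly unrelated. A strong association (25/10/10/25) raises 4.3% only to 4.8%. If the 18 topography subjects are set aside and 20 UB are drawn from the other 52, the best one-factor figure is 22.4%. The joint figure with 13 per cell is 5.0%, or 0.25% for both groups.

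**Step 5: would ordinary stratification meet it?** Proportional allocation sends K × 20/70 of a category to UB: 10.0 for K = 35, 8.6 for K = 30, 7.1 for K = 25. It aims at 10 only if the pool itself is 35/35. In 20,000 simulated trials with sex-by-age strata, 5:2 blocks of 7 and no enrolment caps, exactly 20 UB with 10/10 on both factors occurred in 3.6% (each factor 50/50) or 1.2% (43/57). Stratifying gives approximate balance, not the stated exact one.

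**Step 6: topography subjects.** With 18 per flavour fixed to VLN, 70 − 18 = 52 remain for 50 − 18 = 32 VLN and 20 UB places, a ratio of 8:5. A plain 5:2 list applied to those 52 would yield 52 × 2/7 = 14.9 UB subjects, not 20.

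**The case against.** A reader might infer that allocation must be improperly steered, or that the protection of randomisation is gone. The documents do not support either, for these reasons.

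- The percentages assume unrestricted allocation, which the protocol does not specify. The scheme to be supplied is not described. It could combine enrolment caps with fixed UB slots per sex-by-age cell, for example 5 in each of four cells, and reach 10/10 with no override. This stands: the gap is in what is described, not proof of what will be done.
- The balance sentence is qualified by practicability. This stands for that sentence, but the numerical minimum that follows is not qualified, and the two need reconciling.
- Study group is not defined. If it meant the 70-subject flavour cohorts, the minimum would not bind. The four-group reading is likelier, because Protocol 2.1 and 6.1.1 use group for the VLN and usual brand arms.
- Adjusting on two recorded baseline covariates is not selection on outcome. Allocation also follows enrolment and the Week -1 baseline measurements, so foreknowledge has less scope to shape who enters. This reduces the harm but does not remove it.
- Protocol 6.1.1 sizes the study on within-group change and calls the between-group comparison secondary. Inference uses the per-protocol population, whose exclusions after allocation erode randomised comparability however subjects are allocated. Both points stand, although SAP 7.3 still gives the VLN versus UB contrast a primary label within the mixed model.

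**Conclusion.** The concern holds as a conflict between a stated quota and the allocation method described. With four product groups, the minimum forces exactly 10/10 on two factors in each UB group. Unrestricted allocation delivers that about 4% of the time per UB group and 0.2% in both, given a 35/35 pool with sex and age roughly unrelated, and less often with an uneven pool. For a single factor it is about one in five at best, so the difficulty comes from requiring both factors in both groups.

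Some control beyond chance is therefore needed. The only one described is a person monitoring an open-label allocation, which invites predictable or overridden late assignments. The conclusion rests on the four-group reading and on what the documents disclose; it does not show that the undisclosed scheme is deficient. It is worth settling before enrolment, because it cannot be repaired afterwards.

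**What to change.** In Protocol 4.5:

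1. Replace the monitoring sentence with a pre-generated list, stratified by flavour, sex and age group (40 or under, over 40), with 5:2 allocation. Conceal it centrally, release it one subject at a time, and do not disclose block sizes to sites; a known fixed block of 7 would itself be guessable. Name who holds the list.
2. State how the 18 topography subjects per flavour are handled. One option is to draw them at random from subjects already allocated to VLN at the topography site. The other is to declare them non-randomised and build the list for the other 52 at 32:20.
3. Relax the UB minimum so that exact 10/10 is not required. Alternatively, keep it and meet it by pre-specified enrolment caps with fixed UB slots per stratum.
4. Define study group, and align the non-randomised and randomised descriptions in Protocol 2.1 and SAP 3.

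In SAP 7.3, add sex and age group as fixed effects in the mixed model. Do not add flavour: the four-level product group already encodes it, and the design matrix has rank 8 (4 groups × 2 weeks) with or without it. The pooled comparison can be a contrast within that model.

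The cost is a different list, a few sentences and two model terms. With eight strata, incomplete blocks may move group sizes a few subjects away from 50/20. The caps option instead keeps the sizes but may slow recruitment as cells fill.
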